### **Change from Baseline**

Change from baseline for a given endpoint is defined as the Study Day X value minus the Baseline Value.

### **Days on Study**

Days on study is the number of days from Study Day 1 to the date of study completion or early termination as recorded on the End of Study eCRF page.

### **Days on IMP (Part B)**

Days on IMP is the number of days from Study Day 1 to the date of last dose of IMP as recorded on the End of Treatment eCRF page.

### **Cumulative Dose of IMP (Part B)**

The cumulative dose of IMP is calculated in milligrams and is calculated as the sum of each daily dose on IMP as recorded on the Exposure eCRF page.

### **Treatment-emergent Adverse Event (TEAE)**

Any event reported on the eCRF that occurs on or after the initiation of IMP and up to the final follow-up contact is considered treatment-emergent. Additionally, it is assumed that an Adverse Event which was reported to have started on Day 1 without an associated onset time may have occurred after the initiation of IMP. Hence, Adverse Events occurring on Day 1 with no associated onset time are assumed to be treatment-emergent.

For Part A, treatment-emergent adverse events will be attributed to a period based on the start date. An adverse event starting on or after the initiation of IMP in Period 1 and before dosing with IMP for Period 2, or through follow-up contact if subject discontinues prior to Period 2, is considered a Period 1 TEAE. For Cohort 1 and 2, an adverse event starting on or after the initiation of IMP in Period 2 and before dosing with IMP for Period 3, or through follow-up contact if subject discontinues prior to Period 3 is considered a Period 2 TEAE. An adverse event starting on or after the initiation of IMP in Period 3 and before dosing with IMP for Period 4, or through follow-up contact if subject discontinues prior to Period 4, is considered a Period 3

TEAE. An adverse event occurring after dosing for Period 4, through follow-up contact, is considered a Period 4 TEAE.

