9.4.2. Safety Analyses

Treatment-emergent adverse events, including AEs potentially related to abuse, will be coded according to MedDRA and summarized by treatment, system organ class, and preferred term. Further summaries will be done by seriousness, severity, relationship to IMP, and dose at the time of onset.

Other safety endpoints will be summarized with descriptive statistics by treatment and timepoint, including vital sign measurements, ECG, clinical laboratory assessments and suicidality monitored during the trial using C-SSRS.

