- The investigator will assess the relationship as either of the following:
 - Related: An AE will be considered "related" to the use of the IMP if there is evidence to suggest a
 reasonable possibility of a causal relationship between the IMP and the AE.
 - Not Related: An AE will be considered "not related" to the use of the IMP if there is no plausible causal relationship between the IMP and the AE.
- The investigator will use clinical judgment to determine the relationship.
- Alternative causes, such as underlying disease(s), concomitant therapy, and other risk factors, as well as
 the temporal relationship of the event to trial treatment administration will be considered and
 investigated.
- The investigator will also consult the Investigator's Brochure and/or Product Information, for marketed products, in his/her assessment.
- For each AE/SAE/AESI, the investigator must document in the medical notes that he/she has reviewed
 the AE/SAE/AESI and has provided an assessment of causality.
- There may be situations in which an SAE/AESI has occurred and the investigator has minimal
 information to include in the initial report to the sponsor or designee. However, it is very important
 that the investigator always make an assessment of causality for every event before the initial
 transmission of the SAE/AESI data to the sponsor or designee.
- The investigator may change his/her opinion of causality in light of follow-up information and send an SAE/AESI follow-up report with the updated causality assessment.
- The causality assessment is one of the criteria used when determining regulatory reporting requirements.

Table 17: Follow-Up of AEs and SAEs/AESIs

Follow-Up of AEs and SAEs/AESIs

- The investigator is obligated to perform or arrange for the conduct of supplemental measurements and/or
 evaluations as medically indicated or as requested by the sponsor or designee to elucidate the nature
 and/or causality of the AE or SAE/AESI as fully as possible. This may include additional laboratory
 tests or investigations, histopathological examinations, or consultation with other health care
 professionals.
- If a participant dies during participation in the trial or during a recognized follow-up period, the
 investigator will provide the sponsor or designee with a copy of any post-mortem findings including
 histopathology.
- New or updated information will be recorded in the originally completed eCRF.

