## Concomitant Medications

Concomitant medications are those medications taken on or after the initiation of IMP. These medications include those medications started before the initiation of IMP and continuing post Day 1. Concomitant medications will be classified by treatment. Medications taken during a washout period will be applied to the treatment received immediately prior. Medications taken across multiple treatments will be assigned to those treatments. These medications will be recorded in the Concomitant Medications page of the eCRF.

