### 5.9.1. Adverse Events

Adverse events will be mapped to a Medical Dictionary for Regulatory Activities (MedDRA) version 25.1 or later by system organ class, preferred term, and severity. If a subject experiences multiple events that map to a single preferred term, the greatest Common Terminology Criteria for Adverse Events (CTCAE) toxicity grade and strongest investigator assessment of relation to IMP will be assigned to the preferred term for the appropriate summaries. Events with missing severity or relationship, will be classified as outlined in [Section 4.1.1.1](#).

For Part A, all TEAEs will be attributed to a treatment period based on start date as specified in [Section 4.2.1](#). Any TEAE occurring during the washout period will be attributed to the treatment most recently administered.

The occurrence of TEAEs will be summarized by treatment group for Part A and Part B, using preferred terms, system organ class, and severity. Separate summaries of TEAEs, treatment-emergent serious adverse events (TESAEs), TEAEs by severity, TEAEs related to IMP, AESIs, and events leading to the discontinuation of study will be generated by system organ class and preferred terms. For Part B, a separate analysis of AEs leading to the discontinuation of IMP will be provided.

All AEs reported will be listed for individual subjects showing both verbatim and preferred terms and treatment group at onset of the AE. All AEs that occurred prior to the initiation of IMP will be excluded from the tables but will be included in the listings.

Missing onset dates will be imputed as previously outlined in [Section 4.1.1.2](#) as required to determine treatment-emergent events.

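### Part A adverse events are attributed by start date only, with no rule for an event that is ongoing at the next dose and then worsens

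*SAP*

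**What the plan says.** The definition of a treatment-emergent adverse event in SAP 4.1.2 is broad: "Any event reported on the eCRF that occurs on or after the initiation of IMP and up to the final follow-up contact is considered treatment-emergent". It then fixes the period: "For Part A, treatment-emergent adverse events will be attributed to a period based on the start date". SAP 5.9.1 repeats the rule: "For Part A, all TEAEs will be attributed to a treatment period based on start date as specified in" Section 4.2.1. For the gap between doses it adds: "Any TEAE occurring during the washout period will be attributed to the treatment most recently administered". Protocol 9.4.2 is also onset-based: "Further summaries will be done by seriousness, severity, relationship to IMP, and dose at the time of onset".

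On grading, SAP 5.9.1 says: "If a subject experiences multiple events that map to a single preferred term, the greatest Common Terminology Criteria for Adverse Events (CTCAE) toxicity grade" is used, together with the strongest relationship, for the preferred term in the relevant summaries. It does not say whether this is within a treatment or over all of a subject's periods.

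On recording, Protocol Table 17 says: "New or updated information will be recorded in the originally completed eCRF". Protocol Table 14, however, counts an increase in the frequency or intensity of a pre-existing condition as an adverse event.

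For medications that span periods, the SAP does have a rule: "Medications taken across multiple treatments will be assigned to those treatments".

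**The concern.** Cohorts 1 and 2 form an ascending-dose crossover, and each participant appears in several treatment columns. Treatment-emergent adverse events are a primary endpoint, so severity by dose is a main tolerability result. An event can begin in one period or its washout, still be present at the next dose, and then become more severe. The rules name one period for it, the period of onset. Nothing credits the increase to the dose that preceded it.

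A one-grade shift can matter. Grade 2 gastrointestinal and central nervous system events are events of special interest (Protocol 8.4.6, SAP 3.4.6.1), and SAP 5.9.1 summarizes these separately. A Grade 1 headache that becomes Grade 2 after a later dose therefore crosses a reporting boundary, and the special-interest event could appear under the wrong treatment.

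**Working it through.** The plan states no figure to reproduce. The check covers how often the design steps up, how large one event is, and what the rules produce.

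**1. Transitions.** Protocol Table 8 gives four sequences per cohort, 2 participants each. Writing *up* for active to higher active:

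| Placebo in | Period 1 to 2 | Period 2 to 3 | Period 3 to 4 |
|---|---|---|---|
| Period 1 | placebo to active | up | up |
| Period 2 | active to placebo | placebo to active | up |
| Period 3 | up | active to placebo | placebo to active |
| Period 4 | up | up | active to placebo |

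The cells give 6 up, 3 placebo to active and 3 active to placebo. With 2 participants per sequence these become 12, 6 and 6, or 24 per cohort. Transitions to a higher dose: 12 + 6 = 18, and 18/24 = 75%. Transitions from active to placebo: 6/24 = 25%. The counts are the same with the doses in Protocol Table 10 (0.5, 1.5, 5, 15 mg; 45, 90, 150, 200 mg) taken in ascending order.

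**2. Denominators.** Each period has 6 active and 2 placebo, matching the stated 3:1 ratio. Each dose given once therefore has 6 participants. SAP 5.1 pools placebo across cohorts within a Part: 2 participants × 4 periods × 2 cohorts = 16.

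**3. Size of one event.** 1/6 = 16.7 points at a dose; 1/16 = 6.25, about 6.3 points, on pooled placebo. In Cohort 3, with about 8 participants in each food state, 1/8 = 12.5 points.

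**4. What the rules produce.** Illustration: a headache starts at Grade 1 after 5 mg and reaches Grade 2 after 15 mg, the next dose for that participant. It is the only such event in either column.

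| Handling | 5 mg column | 15 mg column |
|---|---|---|
| One record, carrying its highest grade | 1/6, Grade 2 | 0/6 |
| New record at worsening, maximum within treatment | 1/6, Grade 1 | 1/6, Grade 2 |
| New record at worsening, maximum over all periods | 1/6, Grade 2 | 1/6, Grade 2 |

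All three rows are compatible with the text. The first needs the worsening to stay on the open record and that record to carry its highest grade. The third needs the greatest-grade rule to be read literally, across periods.

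**5. Which row applies.** Table 17 points to the first row, since updates go to the record already completed. Table 14 points to the second or third, if a worsening is treated as an exacerbation and so as a new event, although its wording concerns chronic or intermittent pre-existing conditions. The eCRF completion instructions are not among the documents, so the choice is left open.

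**The case against.** Several points on the other side stand.

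- The outcome is conditional. If the site opens a new record, the start-date rule itself places the worsening under the later dose. Table 17 deals with follow-up information in general and sets no rule on splitting a record by grade.
- The greatest-grade rule is triggered by multiple events under one preferred term, not by one event that changes grade. The summaries are by treatment group, so a maximum within each treatment is the likelier intention.
- A reader might infer that the error always flatters the higher dose. The documents do not support that. In 6 of 24 transitions the next treatment is placebo, and a worsening there would be charged to the active dose. A maximum over all periods could also carry an early high grade forward to a later mild event.
- A reader might extend the dose argument to the food-effect cohort. Both periods there use 50 mg, so only fed versus fasted attribution is at issue.
- The laboratory comparison is only partial. The SAP defines laboratory toxicity by a grade increase from baseline but also attributes it to a period by start date. The period baseline enters through the shift tables in SAP 5.9.4.
- Safeguards exist. All events are listed individually with treatment at onset, events of special interest have narratives, and escalation rests on Safety Review Team review after every dose, not on these tables.

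Rarity is a weaker argument. Doses are at least 5 days apart and eligibility is rechecked each period. But an event that starts late in washout belongs to the earlier treatment and need only be present at the next dose. Exclusion criterion 15 also lets the investigator accept findings judged not medically significant.

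**Conclusion.** The gap is real and worth closing. Start-date attribution is a stated rule, it has no provision for worsening after a later dose, and in Cohorts 1 and 2 three quarters of transitions go to a higher dose. Where the worsening stays on the open record, the later treatment loses it and the earlier one receives it, mostly but not only toward the lower dose or placebo. The greatest-grade wording adds a second ambiguity, which could carry a grade across periods.

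The documents give no frequency, so no overall bias can be stated; the figures of 16.7 and 6.3 points are the weight of a single event. They assume full cohorts of 8, each dose given once, and sequences as in Table 8. Nothing here shows that any escalation decision was affected. The point concerns the final severity-by-treatment and special-interest tables.

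**What to change.** In the TEAE definition (SAP 4.1.2) and in SAP 5.9.1:

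- State that in Part A an adverse event whose grade increases after a later period's dose is also a TEAE of that later period, at the worsened grade. The earlier period keeps the grade reached before that dose.
- State that the greatest grade and strongest relationship are taken within subject, treatment and preferred term.

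A site recording instruction would come too late for Cohorts 1 and 2, because Protocol Version 3.0 describes their dose escalation as complete. For those cohorts, identify events that were ongoing at a later dose and date any grade change by data query. Do this before lock, including the interim Part A lock that SAP 5.12 allows.

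The cost is short SAP text and a few queries. Some events will appear under two treatments, which a table footnote can explain.

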During dose escalation, Cohorts 1 and 2 will employ sentinel dosing (n=2; 1 CVL-354 and 1 placebo) during each period to ensure safety and tolerability before proceeding to dosing of non-sentinel participants for that period. The investigator will review AEs (serious and

nonserious) and all available safety data from the first 24 hours after dosing for the 2 sentinel participants. If clinically significant safety concerns are observed in sentinel participants, dosing of the rest of the cohort will be paused in order for the SRT to discuss the findings and determine subsequent actions. If no safety concerns are observed in the sentinel participants, the investigator will provide written documentation for sponsor confirmation before proceeding to dosing of non-sentinel participants.

Check-in assessments conducted on Day -1 of each period will include both sentinel and non-sentinel participants. No additional check-in assessments will be required for non-sentinel participants prior to dosing if the Check-in assessments are performed within 48 hours prior to dosing.

Each dosing period for the dose escalation portion of Part A will be separated by a washout period of at least 5 days (ie, administration of subsequent doses of investigational medicinal product [IMP] will not occur until at least 5 days after the previous dose of IMP).

Cohorts 1 and 2 will comprise approximately 8 participants each (3:1 ratio of CVL-354 to placebo within each treatment period). All participants will receive single oral doses of CVL-354 or placebo during each period. All doses during dose escalation will be administered under fasted conditions following a 10-hour overnight fast. Participants will continue to fast for 4 hours following dosing on Day 1.

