**Figure 1: Trial Schematic - Part A (Single Ascending Dose, Cohorts 1 and 2)**

Abbreviations: IMP=investigational medicinal product; R=randomization; Seq=sequence.

For each period, Check-in is on Day -1 and Check-out is on Day 3.

Follow-up consists of a contact to check on status 14±3 days after a participant's final dose of IMP in the trial.

Doses/treatment may be modified based on emergent safety, tolerability, and pharmacokinetic data.

Doses may be repeated to confirm safety/tolerability.

[figure not shown]

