##### **4.1.2.2. Analysis Period**

Given the crossover design of Part A, in which each unique subject receives four treatments in a randomly ordered sequence, Period 1 is the subset of study days between the start of dosing for the initial treatment in the sequence until the dosing for Period 2, the second treatment in the sequence. This includes the washout period between dose 1 and dose 2. Period 2 is the subset of study days between the start of dosing for the second treatment until the dosing for Period 3, including the washout period between dose 2 and dose 3. Period 3 is the subset of study days between the start of dosing for the third treatment until the dosing for Period 4, including the washout period between dose 3 and dose 4. Period 4 is the subset of study days between the start of dosing for the fourth period until the end of study.

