## **4.2. Visit Windows**

### **4.2.1. Method of Aligning Measurements to Treatment for Part A (SAD)**

Given the crossover nature of Part A, measurements will be assigned to treatment based on treatment received at each analysis period. The start of a given analysis period will be defined as the time in which a subject takes the first dose of IMP for that analysis period. The end of the

analysis period will be the last measurement taken prior to the start of the next analysis period or the end of the study.

Measurements taken on or after the initiation of IMP in Period 1, and before dosing with IMP for Period 2, or through the end of the study if Period 2 dosing is not initiated, are considered Period 1 measurements, and will be assigned to the treatment randomized or received in Period 1, as appropriate. Measurements taken on or after the initiation of IMP in Period 2, and before dosing with IMP for Period 3, or through the end of the study if Period 3 dosing is not initiated, are considered Period 2 measurements, and will be assigned to the treatment randomized or received in Period 2, as appropriate. Measurements taken on or after the initiation of IMP in Period 3, and before dosing with IMP for Period 4, or through the end of the study if Period 4 dosing is not initiated, are considered Period 3 measurements, and will be assigned to the treatment randomized or received in Period 3, as appropriate. A measurement taken after initiation of dosing for Period 4 is considered a Period 4 event and is assigned to the treatment randomized or received in Period 4, as appropriate.

The 12-lead ECG and vital sign measurements performed pre-dose on Day 1 of each period will serve as the period-specific baseline. For safety laboratory tests, C-SSRS, and vital sign measurements (standing heart rate and blood pressure) not performed pre-dose on Day 1, the assessment performed on the check-in day (Day -1) for each period serves as the baseline value for that period. For [REDACTED] the Predose value for a specific period will serve as the Period Baseline. [REDACTED]

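### In Part A Cohorts 1 and 2 the adverse-event window is open to follow-up only in Period 4, where each cohort's highest listed dose sits, so crude TEAE incidence by dose depends on how the periods were spaced

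*SAP*

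**What the plan says.** The TEAE definition in the SAP (under 4.1.2.4) assigns each Part A event to a period by its start date. The Period 1 window is "An adverse event starting on or after the initiation of IMP in Period 1 and before dosing with IMP for Period 2"; Periods 2 and 3 are defined the same way. A participant who stops before the next dose keeps the window open to the follow-up contact. For the last period the rule is "An adverse event occurring after dosing for Period 4, through follow-up contact, is considered a Period 4 TEAE".

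Two other SAP sections carry the same asymmetry. Section 4.1.2.2 states "Period 4 is the subset of study days between the start of dosing for the fourth period until the end of study", and 4.2.1 states "A measurement taken after initiation of dosing for Period 4 is considered a Period 4 event". Section 5.9.1 adds "Any TEAE occurring during the washout period will be attributed to the treatment most recently administered".

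On spacing, Protocol 4.1.1.1 requires that "administration of subsequent doses of investigational medicinal product [IMP] will not occur until at least 5 days after the previous dose of IMP". This is a minimum, and I find no maximum. The note to SAP Figure 1 reads "Follow-up consists of a contact to check on status 14±3 days after a" participant's final dose.

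Protocol Table 10 lists four ascending levels for each four-period cohort: 0.5, 1.5, 5 and 15 mg, then 45, 90, 150 and 200 mg. SAP 5.9.1 tabulates TEAEs by treatment group, and SAP 5.1 pools placebo across cohorts within a Part. Neither section gives a common post-dose window, a person-time rate or a by-period TEAE table.

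**The concern.** Treatment-emergent adverse events are a primary endpoint, and the by-treatment table is where a reader will look for a relation with dose. Crude incidence rises with the length of observation. In this design the window is set by period, and period is tied to dose. A difference between the top dose and lower doses or placebo can therefore come partly from the calendar.

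Each dose has about 6 active participants, so one participant is about 17 percentage points. A single late background event, counted at one dose and outside the window at another, visibly changes the table.

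Placebo does not absorb this. Every active exposure at 15 mg and 200 mg carries the Period 4 window, but only a quarter of placebo exposures do. The distortion need not look like a smooth dose response: 15 mg has the long window, while the higher 45, 90 and 150 mg doses have the short one.

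**Working it through.** **Inputs from the documents**
- Gap between doses: at least 5 days (Protocol 4.1.1.1).
- Follow-up contact: 14±3 days after the last dose, so 11 to 17 days.
- Screening: 4 weeks in the synopsis, Day -30 in the schedule, so 28 to 30 days.
- Total duration in dose escalation: approximately up to 100 days (Protocol synopsis).
- Each period: 6 active and 2 placebo of 8 participants. Over two cohorts and four periods, placebo has 2 × 4 × 2 = 16 exposures, of which 2 × 2 = 4 are in Period 4.

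**Assumption.** The documents give no background event rate. I use a constant 1%, 2% or 5% per participant-day, with no drug effect.

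**Step 1: window lengths.** At the guaranteed gap, Period 4 is watched 11/5 = 2.2 to 17/5 = 3.4 times as long (14/5 = 2.8 nominally).

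**Step 2: what the stated duration implies.** The 100-day total is the only stated figure that bears on actual gaps. Duration = screening + 1 + 3 × gap + follow-up.
- With 5-day gaps and a day-14 contact: 28 + 1 + 15 + 14 = 58 days, or 60 with 30-day screening.
- Solving 100 days for the gap: (100 − 28 − 1 − 14)/3 = 19 days. Over the ranges above, the result runs from (100 − 30 − 1 − 17)/3 = 17.3 to (100 − 28 − 1 − 11)/3 = 20 days.

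So 5-day gaps do not use up the allowance, and the allowance permits gaps longer than the follow-up.

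**Step 3: incidence with no drug effect.** Incidence = 1 − exp(−rate × days). Pooled placebo = 0.75 × (Period 1–3 incidence) + 0.25 × (Period 4 incidence). With 5-day gaps and a day-14 contact:

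| Assumed rate per day | Lower doses | Top dose | Pooled placebo | Top minus placebo (points, before rounding) |
|---|---|---|---|---|
| 1% | 4.9% | 13.1% | 6.9% | +6.1 |
| 2% | 9.5% | 24.4% | 13.2% | +11.2 |
| 5% | 22.1% | 50.3% | 29.2% | +21.2 |

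At 1% per day, moving the contact to day 11 or day 17 gives 10.4% or 15.6% at the top dose.

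**Step 4: dependence on the gap (top dose minus pooled placebo, points)**

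| Actual gap, days | 1% per day | 2% per day |
|---|---|---|
| 5 | +6.1 | +11.2 |
| 7 | +4.7 | +8.5 |
| 10 | +2.7 | +4.7 |
| 14 | 0 | 0 |
| 18 | −2.6 | −4.4 |

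**Step 5: in participants.** With 6 active participants and 5-day gaps, the expected number with an event at 1% per day is 6 × 0.131 = 0.78 at the top dose and 6 × 0.049 = 0.29 at a lower dose. The chance of at least one is 57% against 26%. At 2% per day it is 81% against 45%.

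**Step 6: after the fix.** With the same window in every period, the window ratio is 1 and the artefact is 0 points at any rate and any gap.

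**The case against.** The strongest reply is that the direction is not fixed. Five days is a floor, and before each escalation the protocol requires sentinel review, tolerability data through 72 hours and a Safety Review Team meeting. Gaps at the minimum are therefore a bounding case, and the 100-day allowance would fit gaps of about 19 days. This stands. A reader might infer that the plan inflates TEAEs at the top dose whatever happens; the documents do not support that.

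Nor do they support saying that Period 4 always holds the top dose. The listed doses point that way for active participants, but 2 of 8 receive placebo in Period 4, and the protocol allows doses to be repeated or lowered. Participants who stop early also carry the long window at lower doses.

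It is also fair that events in the first 5 days are captured equally in every period, that the rates above are assumed, and that at 1% per day the worst case is about half a participant per dose. Late Period 4 events rest on a single remote contact, so detection may be below what a constant rate implies. The trial is descriptive, escalation does not rest on this table, and listings show treatment at onset. These points limit the size and consequence, but they leave the by-dose comparison on unequal observation time.

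A reader might extend the argument to laboratory data, supposing that the next check-in draw counts as an extra post-dose look for Periods 1 to 3. SAP 4.2.1 makes that Day -1 draw the next period's baseline, and the End of Period definition keeps such values out of the laboratory tables. I do not make that claim.

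**Conclusion.** The point holds in conditional form. As written, the Part A by-dose TEAE table compares doses on windows of different length, the length is confounded with dose under the listed ascending scheme, and pooled placebo does not balance it.

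If actual gaps were shorter than about 14 days, crude incidence from background or late-onset events is biased upward at 15 mg and 200 mg. At the 5-day floor the excess over pooled placebo is about 6 points at an assumed 1% per day and 11 points at 2%. Near 14 days it is nil, and beyond that it changes sign.

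These sizes rest on an assumed constant rate, equal detection throughout the window, a day-14 contact and no drug effect. The documents do not give the actual gaps. Protocol 4.1 reports that Cohort 1 and 2 data up to 200 mg have been reviewed, so the sponsor should be able to establish them. This is a cheap improvement to the presentation and does not invalidate the plan.

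**What to change.** In SAP 4.1.2.4 (TEAE definition) and 5.9.1, for Part A Cohorts 1 and 2:
- Add a by-dose TEAE table on one post-dose window common to all periods, for example dose to 120 h, the guaranteed minimum interval (5 × 24 h).
- Show events starting after that window separately, by last dose received.
- Keep the all-events table with its present attribution rule.
- Report the actual window lengths by dose, so that a reader can judge the all-events table.

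The cost is SAP wording and one extra table. No event is dropped, and data collection and dosing are untouched. The downside is that late-onset events, which may be drug-related, appear in a separate display from the common-window comparison; keeping the all-events table beside it covers that.
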